- To assess whether oral insulin may be effective in reducing liver fat content and inflammation in patients with NASH and type 2 DM.

Study Duration

Screening Phase: up to 14 days prior to placebo run-in period

Placebo run-in Phase: 2 weeks

Treatment Phase: 12 weeks

End-of-Study (EOS): After completion of 4 weeks after end of treatment

Study Population and Size

This exploratory study will first enroll 10 patients with NASH and type 2 DM.

At the completion of their 4-week follow-up period, results will be presented to the Helsinki Committee. Following approval, an additional 20 patients will be enrolled. The size of the study population was determined by the investigator (with literature review) to be sufficient to show trends of reducing liver fat content by MRI PDFF (MRI-Proton Density Fat Fraction) images, the FibroMax Test and Fibroscan including CAP.

Inclusion Criteria:

1. Male or female aged 18-70 years.
2. BMI ≥ 25
3. Known type 2 DM according to American Diabetic Association (one of the three needed): Fasting Plasma Glucose ≥ 126 mg/dl or 2h postprandial (PG) following 75g OGTT ≥ 200 mg/dl or HbA1C $> 5.7\%$ ²⁸ or on treatment with metformin
4. Abdominal ultrasound (US) proven fatty liver performed within 6 months before randomization.
5. Fat concentration in the liver of S2 (moderate steatosis, 6–32% hepatocytes with steatosis) or more as measured by Fibromax (SteatoTest and NASHTest Components, BioPredictive, Paris, France²⁹).¹ Or MRI PDFF $> 10\%$.
6. Liver enzyme abnormalities: Up to 5 times ULN.
7. Evidence of \geq stage 3 fibrosis, as determined by FibroScan
8. Signature of the written informed consent.
9. Negative pregnancy test at study entry for females of child bearing potential.
10. Females must have a negative urine pregnancy test result at screening, prior to the start of the run-in period, and at initiation of active dosing. A negative urine and serum pregnancy test must be obtained prior to active dosing. Males and females of childbearing potential must use two methods of contraception (double barrier method), one of which must be an acceptable barrier method from the time of screening to the last study visit (12 weeks). Barrier methods of contraception include male condoms plus spermicide, diaphragm with spermicide plus male condom, cap with spermicide plus male condom, or oral contraceptives. Acceptable methods of birth control include abstinence, oral contraceptives, surgical sterilization, vasectomy, the contraceptive patch, and the contraceptive ring. If a subject is not usually sexually active but becomes active, he or his partner should use medically accepted forms of contraception. Sperm donations will not be allowed for the duration of the study and for 90 days after the last dose of study drug.
Females of non-childbearing potential are defined as postmenopausal who a) had more than 24 months since last menstrual cycle with menopausal levels of FSH, b) who are surgically menopausal (surgical sterility defined by tubal occlusion, bilateral oophorectomy, bilateral salpingectomy or hysterectomy).
11. For hypertensive patients, hypertension must be controlled by stable dose of anti-hypertensive medication for at least 2 months prior to screening (and the stable dose can be maintained throughout the study) with BP $< 150/ < 95$ mmHg
12. Patients previously treated with vitamin E (> 400 IU/day), Polyunsaturated fatty acid (> 2 g/day) or Ursodeoxycholic acid fish oil can be included if drugs are stopped at least 3 months prior to diagnostic liver biopsy and up to the end of the study.
13. Glycaemia must be controlled (Glycosylated Hemoglobin A1c $\leq 8.5\%$) while any HbA1c increment should not exceed 1% during 6 months prior to enrolment).

¹ FibroMax consists of algorithms based on results from the following set of biochemical tests: alpha-2 macroglobulin, haptoglobin, apolipoprotein A1, total bilirubin, ALT, AST, GGT, fasting glucose, triglycerides and total cholesterol. See Poynard, et al., 2005 for discussion of diagnostic value.

Exclusion Criteria

1. Patients with active (acute or chronic) liver disease other than NASH (e.g. viral hepatitis, genetic hemochromatosis, Wilson disease, alpha-1 antitrypsin deficiency, alcohol liver disease, drug induced liver disease) at the time of randomization.
2. ALT or AST > 5 times ULN
3. Abnormal synthetic liver function (serum albumin \leq 3.5gm%, INR >1.3).
4. Known alcohol and/or any other drug abuse or dependence in the last five years.
5. Weight >120 Kg
6. Known history or presence of clinically significant, cardiovascular, gastrointestinal, metabolic (other than diabetes mellitus), neurologic, pulmonary, endocrine, psychiatric, neoplastic disorder or nephrotic syndrome.
7. History or presence of any disease or condition known to interfere with the absorption, distribution, metabolism or excretion of drugs including bile salt metabolites (e.g. inflammatory bowel disease (IBD), previous intestinal (ileal or colonic) operation, chronic pancreatitis, celiac disease or previous vagotomy).
8. Weight loss of more than 5% within 6 months prior to randomization.
9. History of bariatric surgery.
10. Uncontrolled blood pressure BP \geq 150/ \geq 95.
11. Non type 2 DM (type 1, endocrinopathy, genetic syndromes etc).
12. Patients with HIV.
13. Daily alcohol intake >20 g/day for women and >30 g/day for men.
14. Treatment with anti-diabetic medications other than metformin, such as sulfonylurea, DPP-4 inhibitors, GLP-1 receptor agonists, TZDs, etc.
15. Metformin, fibrates, statins, not provided on a stable dose in the last 6 months.
16. Patients who are treated with valproic acid, Tamoxifen, methotrexate, amiodarone.
17. Chronic treatment with antibiotics (e.g. Rifaximin).
18. Homeopathic and/or Alternative treatments. Any treatment must be stopped before the screening period.
19. Uncontrolled hypothyroidism defined as Thyroid Stimulating Hormone >2X the upper limit of normal (UNLN). Thyroid dysfunction controlled for at least 6 months prior to screening is permitted.
20. Patients with renal dysfunction: eGFR < 40 ml/min.
21. Unexplained serum creatinine phosphokinase (CPK) >3X the upper limit of normal (UNL). Patients with a reason for CPK elevation may have the measurement repeated prior to randomization; a CPK retest > 3X ULN leads to exclusion.

STUDY PERIODS

The following parameters will be measured and recorded taken at each of the visits, as specified below:

Screening Phase

Screening process will take place at Visit 1, up to 14 days prior to placebo run in treatment.

Visit 1 (up to week -4)

- Medical history
- Medication history
- Complete Physical examination (PE)
- ECG
- Vital signs (blood pressure, heart rate). Vital signs will be measured in the sitting position after at least 5 minutes of rest.
- Clinical laboratory evaluations
 - Chemistry: Electrolytes, BUN, creatinine, glucose level, liver function tests (LFT) including transaminases (ALT, AST), albumin, and alkaline phosphatases, creatine phosphokinase (CPK)
 - Hematology: Complete blood count (CBC)

Run-in Phase (to week -2)

The run-in phase will consist of 2 weeks period starting at visit (Visit 2) week -2

Visit 2

- Informed consent
- Medication history
- Brief physical examination
- Treatment (run in placebo)
- Vital Signs
- Self-monitored fasting morning blood glucose (finger-stick) of fasting blood glucose will be recorded in the patient diaries 3 days weekly in the morning.

Treatment Phase (week 0)

The Treatment Phase will consist of a treatment period of 12 weeks that will start at visit 3 (week 0) and outpatient visits at week 1, 2, 4, 8, and 12 (final visit).

At each visit patients will have

- Medication history
- Brief Physical examination (PE)- at Visits 4,5, 6, and 7
- Treatment
- Medication Compliance
- Vital signs (blood pressure, heart rate). Vital signs will be measured in the sitting position after at least 5 minutes of rest.

At Visits 3 (baseline), 6, 7, and 8, patients will have

- Clinical laboratory evaluations (chemistry, hematology)
- Fasting blood glucose and insulin (also used for HOMA estimates)²
- Self-monitored fasting morning blood glucose (finger-stick) of fasting blood glucose will be recorded in the patient diaries 3 days weekly in the morning.
- Adiponectin

At Visits 3 and 8 Patients will have

- Complete PE
- FibroMax Test
- Fibroscan
- MRI PDFF

End-of-Study (EOS) (week 16) /Early Discontinuations

The EOS visit (Visit 9) will be conducted 4 weeks following the last scheduled treatment visit. Patients will complete the following EOS evaluations:

- Medication history
- Complete PE, only if the investigator deems it necessary.
- EOS ECG, only if the investigator deems it necessary.
- Vital signs (blood pressure, heart rate) will be measured in the sitting position after at least 5 minutes of rest, only if the investigator deems it necessary.
- Clinical laboratory evaluations (chemistry, hematology)
- Fasting blood glucose
- Fasting blood Insulin
- Adiponectin

Patients who are discontinued early from the study will complete the EOS evaluations at the time of early discontinuation.

Unscheduled visit

The patient may be required to return for an unscheduled visit for a repeat measurement of fasting blood glucose, if the investigator deems it necessary.

² HOMA = The Homeostasis Model Assessment

Self-Monitoring Fasting Blood Glucose and Patient Diaries

All patients will self-monitor fasting morning blood glucose levels three (3) times weekly during the run-in and treatment period. Monitoring must be performed at the same time each designated day (\pm 10 minutes) prior any caloric intake. Patients will be required to record the values in a patient diary and bring the diary to each clinic visit; Information recorded for the fasting blood glucose will be reviewed by the clinical research coordinator for completeness and transcribed onto CRF's. During the study, both fasting finger stick glucose and laboratory fasting plasma glucose will be obtained.

If a fasting blood glucose measures greater than or equal to 270 mg/dL (15 mmol/L) during daily self-monitoring or during any in-clinic visit, the patient will be required to contact the clinic to report the value. Blood will be drawn and sent to lab for plasma glucose determination. The patient may be required to return for an unscheduled visit to the clinic for a repeat measurement of fasting blood glucose within one week after the original measurement. If the repeat measurement is also greater than or equal to 270 mg/dL, the patient will be discontinued from treatment with study drug and offered rescue medication. The patient will continue to be seen for all remaining study visits, if possible.

Fingerstick glucose values of <50 mg/dL (2.78 mmol/L) should be confirmed by laboratory plasma glucose measurements and if three or more are observed within 12 hours subsequent to administration of study drug without a reasonable explanation (such as increased physical activity and/or skipped meal), the patient will be discontinued from treatment with study drug and rescued with glucose administration (20g of glucose tablets) which will be available at all times at the study site. This information will be recorded in the patient's diary and the patient will be instructed to contact the study site if this occurs. The patient will continue to be seen for all remaining study visits. Sites will instruct patients to immediately perform a finger stick glucose measurement if any symptoms occur that may be related to hypoglycemia (e.g., weakness, dizziness, shakiness, increased sweating, palpitations, or confusion), and to avoid delay in treating these symptoms. The measurements will be recorded in the patient diary. Patients will always carry glucose tablets with them and ingest 3-4 tablets if hypoglycemia occurs.

Hypoglycemia and associated symptoms (e.g., weakness, dizziness, shakiness, increased sweating, palpitations, or confusion), have been associated with insulin administration, including ORMD-0801.

Table 1: Schedule of Assessments

Assessments	Screening	Placebo	Treatment						Un Scheduled Visit	End-of-Study / Early Termination
			0	1	2	4	8	12		
Week	up to -4	-2	0	1	2	4	8	12	Not Defined	16
Days	Up to -28	-14	7± 2	7± 2	14± 2	28± 2	56± 2	84± 2		112±2
Visit	1	2	3	4	5	6	7	8	Un Scheduled	9
Written informed consent	X									
Medical history	X									
Medication history	X	X	X	X	X	X	X	X		X
Complete physical examination	X		X					X		(X ¹)
Brief physical examination		X	X	X	X	X	X	X		
Treatment		X	X	X	X	X	X			
Medication compliance check			X	X	X	X	X	X		
ECG	X									(X ¹)
Vital signs	X	X	X	X	X	X	X	X		(X ¹)
Clinical laboratory evaluations ²	X		X			X	X	X	(X ¹)	X
Fasting blood glucose ³		X	X			X	X	X	(X ¹)	X
Fasting Insulin ³		X	X			X	X	X		X
Self-monitored fasting morning blood glucose ⁴		X	X	X	X	X	X	X		
Adiponectin			X			X	X	X		X
FibroMax Test			X					X		
Fibroscan Test			X					X		
MRI PDFF			X					X		

¹Only if investigator deems necessary

²Chemistry (electrolytes, BUN, creatinine, glucose, LFTs) and CBC

³Fasting blood glucose and insulin will be used to determine HOMA estimates.

⁴Self-monitoring (finger-stick) of fasting blood glucose will required 3 days weekly in the morning and recorded in patient diaries.

TREATMENT REGIMEN

The treatment regimen will consist of a soft gelatin capsule containing 8 mg insulin, and 75 mg SBTI. Patients will take 2 capsules daily in the morning with or without food.

SAFETY EVALUATIONS

See complete instructions about Safety and Adverse Events evaluation and reporting in **Appendix B**.

- Adverse events will be collected throughout the study beginning from the time the patient signs the consent form until the EOS evaluations
- Concomitant medications/therapies will be recorded throughout the duration of study, beginning from the time the patient signs the informed consent.
- Vital signs (blood pressure, heart rate) will be measured in the sitting position after at least 5 minutes of rest at all visits
- Clinical laboratory evaluations (chemistry, hematology) will be performed at screening and at weeks 0, 4, 8, 12, and 16.
- Treatment of significant hyperglycemia, will be tailored to the medical history and needs of the patient, as per recommended treatment guidelines.
- Symptomatic hypoglycemia - Hypoglycemia as noted by a feeling of hypoglycaemia with concomitant blood glucose measurements below 70.
 - All occurrences of hypoglycemia will be treated with orange juice, 3-4 glucose tablets, or a 20% glucose solution via an I.V. bolus injection over 1 to 2 minutes and the subject will be monitored until symptoms have resolved.
 - If three or more finger stick glucose values of <50 mg/dL (2.78 mmol/L) are observed in one week within 12 hours subsequent to administration of study drug without a reasonable explanation (such as increased physical activity and/or skipped meal), the patient will be discontinued from treatment with study drug. This information will be recorded in the patient's diary and the patient will be instructed to contact the study site if this occurs. The patient will continue to be seen for all remaining study visits.
 - The site will instruct patients to immediately perform a finger stick glucose measurement if any symptoms occur that may be related to hypoglycemia (e.g., weakness, dizziness, shakiness, increased sweating, palpitations, or confusion), and to avoid delay in treating these symptoms. The measurements will be recorded in the patient diary.
 - Patients will always carry glucose tablets with them and ingest 3-4 tablets if hypoglycemia necessitates it.

REFERENCES

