Definite: The event follows a reasonable temporal sequence from the time of active study drug administration, follows a known response pattern to the drug, cannot be reasonably explained by other factors such as the patient’s condition, concomitant drugs or therapeutic interventions, AND either occurs immediately following active study drug administration, improves on stopping the study drug, or reappears on re-exposure.

Adverse Events of Hypoglycemia

The CTCAE (version 4.0) criteria for mild, moderate, and severe hypoglycemia based on blood glucose will be used, as shown below:

Mild: < 70 – 55 mg/dL (< 3.8 - 3.0 mmol/L)

Moderate: < 55 – 40 mg/dL (< 3.0 - 2.2 mmol/L)

Severe: < 40 – 30 mg/dL (< 2.2 - 1.7 mmol/L)

Life Threatening: < 30 mg/dL (< 1.7 mmol/L)

Recording Adverse Events

All adverse events experienced during the trial, regardless of relationship to study medication, must be recorded on the Adverse Event CRF from the time of patient consent until completion of patients End of Study visit (Visit 9). All serious adverse events will be collected through Visit 9. The Investigator must continue to follow all non-serious events possibly related to the study medication and all serious adverse events until they resolve or until the Investigator assesses them in writing as chronic or stable.

Regardless of relationship to study medication, the event must be recorded on the Adverse Event CRF. Adverse event documentation should include the following information:

- Standard medical terminology for the AE
- Description of adverse event
- Date and time of onset
- Date and time of resolution of the adverse event
- Whether or not the event is ongoing
- Severity of the event
- Relationship between the adverse event and the investigational product
- Description of any actions taken (e.g., medications, treatments)
- Outcome of the AE
- Whether or not the effect was serious and/or unanticipated

Whenever possible, a diagnosis should be given when signs and symptoms are due to common etiology (e.g., cough, runny nose, sneezing, sore throat, and head congestion should be reported as "upper respiratory infection"). For the purposes of this study, hypoglycemic events will be considered adverse events and should be recorded in source and CRF records.

When a diagnosis is not available, each adverse event should be reported separately. For example, "nausea and vomiting" should be split into two separate events.

Reporting Serious Adverse Events

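### The contraception rule (inclusion item 10) counts oral contraceptives as a barrier method and dates the last study visit at 12 weeks, when it is Visit 9 at week 16

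*Protocol*

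**What the plan says.** **Methods.** Protocol, Inclusion Criteria, item 10, states that males and females of childbearing potential "must use two methods of contraception (double barrier method), one of which must be an acceptable barrier method". It then gives two lists. The barrier list has three entries that each include a male condom, and a fourth entry, oral contraceptives. The list of acceptable methods names oral contraceptives again, with abstinence, sterilization, vasectomy, patch and ring.

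**Period.** The same item sets the period as "from the time of screening to the last study visit (12 weeks").

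**Schedule.** The Treatment Phase section plans "outpatient visits at week 1, 2, 4, 8, and 12 (final visit"). The End-of-Study section, headed week 16, adds: "The EOS visit (Visit 9) will be conducted 4 weeks following the last scheduled treatment visit". Study Duration agrees ("After completion of 4 weeks after end of treatment"). Table 1 puts Visit 8 at week 12 and Visit 9 at week 16, under "End-of-Study / Early Termination". Appendix B records adverse events "until completion of patients End of Study visit (Visit 9").

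**Related precautions.** Appendix B says that it is unknown whether the drug can harm a fetus when given to a pregnant woman, and that no animal reproductive studies have been done. It asks for reports of pregnancies up to 30 days after the drug is stopped. Item 10 bars sperm donation for 90 days after the last dose.

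**The concern.** Item 10 is an instruction that sites and patients act on, so its literal content matters.

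An oral contraceptive is not a barrier. Once it sits in the barrier list, the demand for a barrier can be met without one, and this holds for the whole dosing period. Item 10 asks for pregnancy tests up to the start of active dosing, and Table 1 shows none at later visits. During treatment the contraception rule is therefore the main stated safeguard.

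The end of the period is also unclear. The words name the last study visit, while the number names the end of treatment. A site that follows the number lets contraception stop at Visit 8; a site that follows the words carries it to Visit 9.

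**Working it through.** **1. Can the barrier requirement be met without a barrier?**

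- Requirement: two methods, at least one from the barrier list.
- Take oral contraceptives (barrier list) and the patch or the ring (acceptable-methods list). Both conditions are met and no physical barrier is used.
- The phrase about a double barrier does not settle the matter. Two barriers and at least one barrier are different requirements, and item 10 states both. The second list, which names no physical barrier, would have little purpose if both methods had to be barriers. The text as a whole therefore fits one barrier better than two.

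**2. Does 12 weeks match the last study visit?**

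Inputs from Table 1 (nominal days): Visit 8 = day 84; Visit 9 = day 112. Inputs from Study Duration: treatment 12 weeks; follow-up 4 weeks.

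- Last study visit: 12 + 4 = week 16. The stated 12 is not reproduced.
- End of treatment: 84 / 7 = week 12. The stated 12 matches Visit 8.
- Discrepancy: 112 − 84 = 28 days = 4 weeks, all after the end of dosing.

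**3. How does week 16 sit with the 30-day pregnancy-reporting window?**

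- For a patient who completes treatment, Visit 9 falls nominally 28 days after Visit 8, and 30 − 28 = 2 days short of the window.
- For a patient who leaves the study early, the End-of-Study evaluations are done at the time of discontinuation. That patient's last visit can fall close to the last dose, so naming Visit 9 alone would leave the period undefined or very short. This group needs an end point tied to the last dose.
- A patient who stops the drug under the glucose rules but stays in follow-up still has Visit 9.

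**The case against.** The strongest reply is that both errors are slips which a sensible reader would resolve. The Treatment Phase section itself calls week 12 the final visit, so the 12 in item 10 probably means Visit 8. Dosing is covered whether the rule ends at Visit 8 or Visit 9. The Protocol nowhere says that contraception is needed in the 4 weeks off drug: its statement on fetal harm concerns administration to a pregnant woman, and the 30-day window is for reporting, not contraception. On methods, two listed methods are still required, and the mention of a double barrier points to a strict intent.

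Much of this stands. The gain from correcting the end point is small, and the Protocol does not show which visit was meant. But the final-visit label belongs to the treatment phase and does not make week 12 the last study visit. The mention of a double barrier leaves oral contraceptives in the barrier list and adds a second contradiction.

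A reader might infer more than the Protocol supports:

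- *That contraception lapses during dosing.* Twelve weeks counted from screening would end at study week 8 to 10 (day −28 + 84 = 56; day −14 + 84 = 70). But the number stands directly after the visit it labels, and the schedule labels visits by study week. Elapsed time from screening is an unlikely reading.
- *That patients are left unprotected.* The literal rule still requires two methods, and nothing in the Protocol quantifies a loss of protection from pairing a pill with a patch or ring.
- *That the 90-day limit on sperm donation sets the length of contraception.* It is a separate rule, and the Protocol does not extend it.

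**Conclusion.** Item 10 is wrong as written in two places and should be corrected.

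The misplaced entry in the barrier list is the more important error. It defeats a stated requirement for the whole 12 weeks of dosing. This conclusion rests only on the wording of item 10 and on an oral contraceptive not being a barrier.

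The visit label is off by 4 weeks (week 12 against week 16). The consequence is modest because the gap lies entirely after dosing. Preferring Visit 9 assumes that the words naming the last study visit govern over the number in parentheses. The 30-day pregnancy-reporting window fits that choice but does not prove it.

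Neither error touches the sample size, the visit schedule or any analysis.

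**What to change.** Amend item 10 as follows:

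1. Delete oral contraceptives from the barrier list and leave them in the list of acceptable methods.
2. Delete the parenthesis about a double barrier, so that the rule reads consistently as two methods with at least one barrier. If the sponsor does intend two barriers, the clause asking for one must be rewritten instead.
3. Replace the 12-week label with: End-of-Study, Visit 9, week 16, or, for patients who discontinue early, at least 30 days after the last dose. If the sponsor wants completers to cover the full reporting window too, 30 days after the last dose can be set as a minimum for everyone.

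The cost is a wording amendment to one criterion, and to the patient information if it repeats this text. No visit, test or patient is added.

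### Consent is at Visit 1 in Table 1 but at Visit 2 in the text, the pregnancy tests ordered by inclusion 10 are not scheduled, and inclusions 5 and 7 do not say which dated results settle them

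*Protocol*

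**What the plan says.** **Consent.** Table 1 (Schedule of Assessments) has a row "Written informed consent" with a single mark, in the Screening / Visit 1 column. In the text under Study Periods, the Visit 1 list has no consent item, and "Informed consent" is the first item of the Visit 2 list. Safety Evaluations and Appendix B (Recording Adverse Events) both start adverse-event recording at the patient's consent.

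**Pregnancy tests.** Inclusion 10 requires negative urine tests at screening, before the run-in and when active dosing begins, and a urine and serum test before active dosing. Inclusion 9 requires a negative test at study entry.

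**Liver tests.** Inclusion 5 is met by steatosis of grade S2 "or more as measured by Fibromax (SteatoTest and NASHTest Components", or by MRI PDFF above 10%. Inclusion 7 is met by FibroScan. The text lists all three tests under "At Visits 3 and 8 Patients will have", and Table 1 marks them at weeks 0 and 12 only. On screening the text says: "Screening process will take place at Visit 1, up to 14 days prior to placebo run in treatment". The 12-week treatment period begins at Visit 3. Only the ultrasound criterion, inclusion 4, has a look-back period: "Abdominal ultrasound (US) proven fatty liver performed within 6 months before randomization".

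**The concern.** A site works from the visit lists and Table 1. If these disagree with each other, or leave out something that the eligibility section orders, what is done depends on which page the site follows.

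Three things are at stake. Under the text version, study procedures come before consent, and the start of adverse-event recording moves with the consent date. A site that follows the schedule alone would perform none of the pregnancy tests, although Appendix B says that it is not known whether the product can cause fetal harm and that pregnant women are excluded. Finally, no scheduled liver reading settles inclusions 5 and 7 before the run-in, and the protocol does not say what does.

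**Working it through.** The protocol states no sample-size or power figure that bears on this point. The check is a cross-reading of the sections, with a short timeline.

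**1. Consent**

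| Item | Text, Study Periods | Table 1 |
|---|---|---|
| Consent | Visit 2 | Visit 1 |
| Medical history | Visit 1 | Visit 1 |
| Complete physical examination (first) | Visit 1 | Visit 1 |
| ECG (first) | Visit 1 | Visit 1 |
| Clinical laboratory tests (first) | Visit 1 | Visit 1 |

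The medical-history row of Table 1 has the same layout as the consent row, and the text confirms Visit 1 for it. A shifted table column is therefore an unlikely explanation. Only consent differs.

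Timeline, ignoring the visit windows of 2 days either way:
- Screening is up to 14 days before the run-in, and the run-in lasts 14 days. Visit 1 is then at day -(14 + 14) = -28 at the earliest, which agrees with Table 1. Visit 2 is at day -14.
- Largest gap between the two consent dates: 28 - 14 = 14 days.
- Adverse-event recording runs to the end-of-study visit at day 112. It lasts up to 28 + 112 = 140 days with consent at Visit 1, and 14 + 112 = 126 days with consent at Visit 2.
- The 14 days of run-in and the 112 days from week 0 are covered in both versions.

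**2. Pregnancy tests**

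| Required by inclusion 10 | In a visit list | In Table 1 |
|---|---|---|
| Urine, screening | no | no |
| Urine, before the run-in | no | no |
| Urine, start of active dosing | no | no |
| Serum, before active dosing | no | no |

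The first two rows could be read as one time point (screening, being before the run-in). The requirement is then two urine time points instead of three, and the number scheduled is still zero. The laboratory panel does not cover the tests either: the Visit 1 list and footnote 2 of Table 1 define it as chemistry and blood count, with no pregnancy test.

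**3. Inclusions 5 and 7**

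| Criterion | Deciding test | First scheduled | Look-back stated |
|---|---|---|---|
| 4 | Ultrasound | not scheduled | 6 months |
| 5 | FibroMax or MRI PDFF | Visit 3 | none |
| 7 | FibroScan | Visit 3 | none |

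Because inclusion 5 offers alternatives, two tests are enough to settle both criteria: FibroScan, and either FibroMax or MRI PDFF. None of the three has a scheduled reading before Visit 3. The Visit 1 bloods cannot stand in for FibroMax, because the footnote on FibroMax requires alpha-2 macroglobulin, haptoglobin and apolipoprotein A1, which the Visit 1 list does not name.

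Two readings remain. If the Visit 3 results decide eligibility, the patient has already completed two weeks of placebo. If earlier results decide it, the protocol does not say so, and a result of any age qualifies.

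**The case against.** The strongest reply concerns the liver tests. Text and Table 1 agree on Visits 3 and 8, and inclusions 5 and 7 name a method but no visit. The protocol plainly assumes earlier work-up: inclusion 4 accepts a past ultrasound, inclusion 12 refers to a diagnostic liver biopsy that is on no schedule, and inclusion 13 needs six months of HbA1c history. This stands. A reader might infer that the schedule contradicts inclusions 5 and 7, but the documents support only that the source and date of the qualifying results are not stated. Nor does anything say that active dosing comes before the Visit 3 assessments on the day, so the exposure in question is to placebo.

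A reader might also count HbA1c, TSH and INR as contradictions because no laboratory list names them. They are incomplete detail. Inclusion 3 can be met without HbA1c, the thyroid exclusion allows for disease controlled before screening, and the open wording on liver function tests might cover INR. Other exclusions, such as viral hepatitis and HIV, also have no named test and may rest on medical history.

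A third inference is that the Visit 3 readings both select patients and serve as baseline, so that regression to the mean would inflate the apparent fall in liver fat in a study with no control arm. No passage says that the Visit 3 readings select. The size would depend on repeatability and pass rates that the protocol does not give, and it could be practically zero. It is not part of this point.

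None of this answers the consent conflict or the missing pregnancy tests.

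**Conclusion.** The point holds with different strength in its three parts.

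- **Consent** is a direct contradiction between the text and Table 1. As the text is written, examination, ECG and bloods come before consent, and adverse-event recording starts up to 14 days later than under Table 1.
- **Pregnancy tests** are a direct mismatch: two or three urine time points and one serum test are ordered, and none is scheduled.
- **Inclusions 5 and 7** have an unstated source and window for the qualifying results. Unless earlier results are meant, a patient can finish the run-in before either criterion is settled.

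A reader might conclude that the differing consent dates bias the primary safety objective. They do not: the days in dispute come before any study capsule, and both versions record the run-in, treatment and follow-up in full. The point should be fixed because it affects subject protection and the eligibility record. It rests on the protocol's own text and on Table 1 as extracted, and on no outside figure.

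**What to change.** 1. Reconcile the text with Table 1: put consent first in the Visit 1 list, before any study procedure, and remove it from the Visit 2 list.
2. Enter the urine and serum pregnancy tests that inclusion 10 already orders in the visit lists and as a row of Table 1, and make clear whether screening and pre-run-in are one time point or two.
3. State that inclusions 5 and 7 are settled before the run-in from dated earlier results within a stated window, and that the Visit 3 readings serve as baseline. Tie the window to a named visit: the one in inclusion 4 runs to randomization, a step that this open study does not describe.
4. As a minor completion, name HbA1c, TSH and INR in the screening bloods.

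The cost is one amendment of the protocol text and Table 1, and a few screening bloods. The pregnancy tests add nothing beyond what is already required. No extra FibroMax, FibroScan or MRI is needed where a dated result exists. A patient without one would need the missing test before the run-in, and the documents do not allow that number to be estimated.
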